1.4 Correlative Studies

1.4.1 Pharmacogenetics

The genes that have been associated with irinotecan pharmacodynamic and pharmacokinetic pathways include those responsible for activation, inactivation and transport of the drug. These genes include *ABCB1*, *ABCC2*, *ABCG2*, *BCHE*, *CES1*, *CES2*, *CYP3A4*, *CYP3A5*, *SLCO1B1*, *TOPI*, *UGT1A1*, *1A3*, *1A4*, *1A6*, *1A7*, *1A8*, *1A9* and *UGT1A10*. As NKTR-102 is a conjugate of irinotecan, most of the irinotecan pathway genes may interact with it thus resulting in similar phenotypic effects. Hence, several genetic variants associated with the pathways may contribute to the clinical outcome of NKTR-102 therapy.

Some of the well-known genetic variants that have been associated with irinotecan clinical outcomes include the polymorphic repeat in *UGT1A1* promoter region (*UGT1A1**28, rs8175347; *UGT1A1**93) and the *ABCB1* (1236C > T, 2677G > T/A, 3435C > T), *ABCC2* (-24C > T, 1249G > A, 3972C > T), and *ABCG2* (34G > A, 421C > A) polymorphisms. It is reported that nearly 50% of the variations in neutropenia among individuals could be explained by a combination of genetic polymorphisms and non-genetic covariates, with gene combinations attributing to 28% of the variations, suggesting a polygenetic basis for neutropenia.³² *UGT1A1**28 and *93 genotypes have been associated with toxicity; *ABCC2* 3972C > T with severe diarrhea in both Korean and European patients while *SLCO1B1**5 allele is reported to be associated with increased risk of severe neutropenia in Asians, and the *SLCO1B1**1b allele is suggested to be protective of neutropenia.³²⁻³⁵

This Phase II study (38 patient samples) will initially focus, in an exploratory manner, on the primary genes which will activate (*CES1*, *CES2*, *CYP3A4*, and *CYP3A5*) and inactivate (*UGT1A1*) NKTR-102. It is hypothesized that germline polymorphic variants in *CES1*, *CES2*, *CYP3A4*, *CYP3A5* and *UGT1A1* may affect toxicity as well as response to NKTR-102 therapy.

SNP Identification: We will generate tagSNPs from National Center for Biotechnology Information (NCBI), HapMap and/or the Genome Variation Server databases using the Caucasian SNP information for these 5 genes in addition to using SNPs previously reported in literature. These SNPs will be selected with sufficient frequency that its impact on the clinical outcome at a population level would be meaningful and have some degree of likelihood to alter the function of the gene in a biologically relevant manner. Fifty-three SNPs have been identified for genotyping.

Genotyping: The tagSNPs will be genotyped using the MassARRAY Compact system (Sequenom) at RPCI as previously described.³⁶ Whenever possible, the published methods and primers will be used for polymorphic variants such as *UGT1A1**28.

1.5 Risks Associated with NKTR-102

A majority of NKTR-102 related treatment-emergent adverse events (TEAEs) occurred in the system organ class (SOC) of GI disorders with diarrhea experienced most commonly by 85.5% of patients, followed closely by nausea (77.6%), fatigue (51.3%), and vomiting (48.7%). Other clinically significant NKTR-102-related TEAEs with an incidence rate > 10% included anorexia, dehydration, alopecia, electrolyte disturbances like hypokalemia and hypomagnesemia,

abdominal pain, anemia, and blurred vision, in decreasing order of frequency. Prolonged severe diarrhea with dehydration leading to pre-renal azotemia and subsequent acute renal insufficiency has been fatal in three patients in the ongoing Phase II studies in metastatic colorectal, ovarian, and breast cancers (one patient in each study). To date, early onset cholinergic diarrhea (as seen with irinotecan) has not been observed in any patient who received NKTR-102. Given the extended $t_{1/2}$ of SN38 derived from NKTR-102 (approximately 50 days), late onset diarrhea may occur and can be life-threatening if treatment is delayed. Early, proactive, and aggressive intervention with anti-diarrheal therapy, IV hydration, and maintenance of electrolyte balance is essential to prevent volume depletion, electrolyte imbalances, and the development of kidney failure.

Myelosuppression, especially neutropenia, can occur in patients receiving NKTR-102. Neutropenia in the setting of dehydration and unresolving GI toxicities may lead to the development of life-threatening or fatal sepsis. To date across all clinical studies, three patients have died within 30 days from last dose of NKTR-102 due to potentially drug-related neutropenic sepsis or complications of neutropenic sepsis, such as septic shock.

Prior to retreatment, patients must meet minimal requirements with respect to hematopoietic function especially neutrophil count with an ANC of $\geq 1.5 \times 10^9/L$. Except for diarrhea (complete resolution of diarrhea to Grade 0 should be present for at least seven days without the need for anti-diarrheal medications and/or supportive care prior to retreatment with NKTR-102), all Grade 3 or higher toxicities must resolve to baseline or Grade 1 severity prior to retreatment. Supportive care may be implemented in order to ameliorate diarrhea, nausea, vomiting, anorexia, or myelosuppression. Dose reductions must also be implemented for patients who experience recurrent or specific severe toxicities as defined by the dose modification guidelines included in each protocol.

Hypersensitivity or mild allergic reactions characterized by itching, flushing, dizziness, muscle twitching, and/or temporary speech impairment have been observed in some patients. In most cases, symptoms were mild in severity and management with antihistamines and/or steroids led to successful resolution of these events. In many patients, NKTR-102 rechallenge has been successful in subsequent cycles of therapy following premedication with antihistamines and/or corticosteroids.

2 RATIONALE

Small-cell lung cancer (SCLC) is one of the most aggressive and lethal cancers in humans. Although standard combination cytotoxic chemotherapy agents have shown antitumor activity with initial responses seen in 70% - 90% for both limited and extensive stages of SCLC, long-term survival is low and most patients eventually develop progressive disease within the first 2 years. Moreover, among patients who relapse, prognosis remains poor with second-line therapy (**Table 1**).

Etirinotecan pegol (NKTR-102) is a targeted, long-acting topoisomerase-I inhibitor designed to provide continuous exposure to SN38 (7-ethyl-10-hydroxycamptothecin), while reducing excessively high irinotecan and SN38 plasma concentrations associated with toxicities upon administration of irinotecan. Preclinical and clinical studies have shown that the half-life of

active drug generated from NKTR-102 is greatly extended to 50 days and that active drug remains in circulation throughout the entire chemotherapy cycle, providing sustained exposure to active metabolite of irinotecan (SN38). We propose to investigate the efficacy of NKTR-102 against relapsed or refractory small cell lung cancer.

3 OBJECTIVES

3.1 Primary Objective

The primary objective of this study is to evaluate the 18-week progression free survival (PFS) rate of relapsed SCLC patients treated with NKTR-102.

3.2 Secondary Objectives

- To evaluate the objective response rate.
- To evaluate the duration of response.
- To evaluate the overall survival.
- To evaluate the toxicity of NKTR-102 in this patient population.

3.3 Correlative Objective

- To explore the correlation between UGT1A1 polymorphisms and NKTR-102 toxicities.

4 METHODOLOGY

4.1 Study Design

This is a single stage Phase II study of relapsed small cell lung cancer patients who have received only one prior systemic therapy regimen. There will be 2 patient cohorts: those progressing on first-line therapy < 3 months after completion of treatment (Group A: chemo resistant) and those progressing on first-line therapy \geq 3 months after completion of treatment (Group B: chemo sensitive). Eirinotecan pegol will be administered at 145 mg/m² IV once every 3 weeks. Cycles will be repeated every 21 days (\pm 3 days) until disease progression. Patients who develop metastases in the central nervous system (CNS) as the only site of disease progression could receive therapeutic whole brain radiation therapy (WBRT), or gamma knife radiosurgery and after completion of WBRT continue on NKTR-102. Imaging studies are scheduled to be obtained after every other 21-day cycle.

4.2 Target Accrual and Study Duration

A maximum of 38 subjects (20 patients from Group A and 18 patients from Group B) at multiple sites, including RPCI will be enrolled. Accrual is expected to take up to 4 years. Patients will be on study for approximately 18 – 24 months.

5 SUBJECT SELECTION

5.1 Inclusion criteria

Each prospective subject must meet ALL of the following inclusion criteria in order to be eligible for this study (except where noted):

1. Written informed consent granted prior to initiation of any study-specific screening procedures, given with the understanding that the patient has the right to withdraw from the study at any time, without prejudice.
2. 18 years of age or older.
3. Histologic or cytologic diagnosis of SCLC. (Note: Patients with mixed histology are not eligible.)
4. ECOG performance status of 0 or 1 (refer to **Appendix B**).
5. Presence of measurable disease as defined in with ≥ 1 lesion whose longest diameter can be accurately measured as ≥ 20 mm with conventional techniques or as ≥ 10 mm with spiral CT.
6. Previously treated SCLC with only one prior treatment regimen [cyclophosphamide/doxorubicin/vincristine (CAV) alternating with etoposide/cisplatin (EP) is acceptable].
7. Resolution of all acute toxic effects of prior chemotherapy, radiotherapy, hormonal therapy, or surgery to NCI-CTCAE version 4.0 Grade ≤ 1 , except for diarrhea (which must be grade 0 without supportive antidiarrheal medications) and alopecia (any grade).
8. Adequate hematologic, liver, and renal function, defined as:
 - Platelet count $\geq 100 \times 10^9/L$
 - Hgb ≥ 9 gm/dL
 - Absolute neutrophil count (ANC) $\geq 1500/\mu L$
 - Serum creatinine ≤ 1.5 mg/dL or creatinine clearance > 45 mL/min. Use either measured or calculated with Cockcroft -Gault formula (**Appendix C**)
 - Serum total bilirubin ≤ 1.5 x ULN
 - Aspartate Transaminase (AST) and alanine transaminase (ALT) ≤ 3 x ULN or ≤ 5 x ULN if caused by liver metastasis
9. Women of childbearing potential must have a negative pregnancy test performed within seven days prior to the start of study drug. Male and female subjects of child-bearing potential must agree to use double-barrier contraceptive measures, or avoidance of intercourse during the study and for 6 months after last investigational drug dose received

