			3. Histologic or cytologic diagnosis of SCLC. (Note: Patients with mixed histology are not eligible.)	
			4. ECOG performance status of 0 or 1 (refer to Appendix B).	
			5. Presence of measurable disease as defined by ≥ 1 lesion whose longest diameter can be accurately measured as ≥ 20 mm with conventional techniques or as ≥ 10 mm with spiral CT.	
			6. Previously treated SCLC with only one prior treatment regimen [cyclophosphamide/doxorubicin/vincristine (CAV) alternating with etoposide/cisplatin (EP) is acceptable].	
			7. Resolution of all acute toxic effects of prior chemotherapy, radiotherapy, hormonal therapy, or surgery to NCI-CTCAE version 4.0 Grade ≤ 1 , except for diarrhea (which must be Grade 0 without supportive antidiarrheal medications) and alopecia (any grade).	
			8. Adequate hematologic, liver, and renal function, defined as: 
 • Platelet count $\geq 100 \times 10^9/L$ • Hgb ≥ 9 gm/dL • Absolute neutrophil count (ANC) $\geq 1500/\mu L$ • Serum creatinine ≤ 1.5 mg/dL or creatinine clearance > 45 mL/min. Use either measured or calculated with Cockcroft - Gault formula (Appendix C). • Serum total bilirubin ≤ 1.5 x ULN • Aspartate Transaminase (AST) and alanine transaminase (ALT) ≤ 3 x ULN or ≤ 5 x ULN if caused by liver metastasis 	
			9. Women of childbearing potential must have a negative pregnancy test performed within seven days prior to the start of study drug. Male and female subjects of child-bearing potential must agree to use double-barrier contraceptive measures, or avoidance of intercourse during the study and for 6 months after last investigational drug dose received.	

Study participant meets all entry criteria: Yes No

Investigator Signature: _____ Date: _____

INVESTIGATOR STUDY ELIGIBILITY VERIFICATION FORM

Subject Name: (Network sites use subject initials): _____

Medical Record No.: (Network sites use subject ID): _____

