8.2 Target Lesions

All measurable lesions up to a maximum of 2 lesions per organ and 5 lesions in total, representative of all involved organs, will be identified as target lesions and recorded and measured at baseline. Target lesions will be selected on the basis of their size. Lesions with the longest diameter (short axis for lymph nodes) and are ≥ 10 mm (CT and MRI), ≥ 15 mm lymph nodes, > 20 mm CXR and are for accurate repetitive measurements (either by imaging techniques or clinically) will be chosen. A sum of the longest diameter (short axis for lymph nodes) of all target lesions will be calculated and reported as the baseline sum diameters. This will be used as reference to further characterize the objective tumor response of the measurable dimension of the disease.

- **Complete Response (CR):** Disappearance of all target lesions. Any lymph nodes must have a reduction in short axis to < 10 mm. Changes in tumor measurements must be confirmed by repeat studies performed no less than 6 weeks after the criteria for response are first met.
- **Partial Response (PR):** At least a 30% decrease in the sum of diameters of target lesions, taking as reference the baseline sum diameters. Changes in tumor measurements must be confirmed by repeat studies performed no less than 6 weeks after the criteria for response are first met.
- **Progressive Disease (PD):** At least a 20% increase in the sum of diameters of target lesions, taking as references the smallest sum on study (this includes the baseline sum if that is the smallest on study). In addition to the relative increase of 20%, the sum must also demonstrate an absolute increase of at least 5 mm. The appearance of one or more new lesions is also considered progression.
- **Stable Disease (SD):** Neither sufficient shrinkage to qualify for PR nor sufficient increase to qualify for PD, taking as reference the smallest sum diameter while on study. Subjects having a documented response with no confirmation of the response will be listed with stable disease.

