8.3 Non-Target Lesions

All other small lesions (longest diameter < 10 mm or lymph nodes ≥ 10 mm to < 15 mm short axis) and non-measurable lesions (i.e., leptomeningeal disease, ascites, pleural or pericardial effusion, inflammatory breast disease, lymphangitic involvement of skin or lung, blastic bone lesions, or abdominal masses/abdominal organomegaly identified by physical exam that is not measurable by imaging) should be identified as non-target lesions and indicated as present in the source documents at baseline. The general location will also be documented on the images drawing a regularly-shaped Region of Interest. Measurements of the non-target lesions will not be performed, but the presence or absence of each should be noted throughout follow-up and evaluation.

- **Complete Response:** Disappearance of all non-target lesions and normalization of tumor marker level, if applicable. All lymph nodes must be non-pathological in size (< 10 mm short axis).
- **Non-Complete Response/Non-Progressive Disease:** Persistence of 1 or more non-target lesion(s) and/or maintenance of tumor marker level above the upper limits of normal.
- **Progressive Disease:** Appearance of 1 or more new lesions or the unequivocal progression of existing non-target lesions. Although a clear progression of non-target lesions is exceptional, in such circumstances, the opinion of the treating physician should prevail and the progression status should be confirmed at a later time.

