8.4 Evaluation of Response

Time point response assessments will be performed every other cycle (timed to coincide with the end of a cycle) with a confirmatory assessment (required for non-randomized trials) no less than

4 weeks after a PR or CR is deemed. To determine time point response, refer to **Table 5** and **Table 6**.

Table 5. Time Point Response Criteria (+/- non-target disease)

Target Lesions	Non-Target Lesions	New Lesions	Overall Response
CR	CR	No	CR
CR	Non-CR/Non-PD	No	PR
CR	Not evaluated	No	PR
PR	Non-PD or not all evaluated	No	PR
SD	Non-PD or not all evaluated	No	SD
Not all evaluated	Non-PD	No	NE
PD	Any	Yes or No	PD
Any	PD	Yes or No	PD
Any	Any	Yes	PD

Table 6. Time Point Response Criteria (non-target disease only)

Non-Target Lesions	New Lesions	Overall Response
CR	No	CR
Non-CR/non-PD	No	Non-CR/non-PD ¹
Not all evaluated	No	NE
Unequivocal PD	Yes or No	PD
Any	Yes	PD

¹ Non-CR/non-PD is preferred over SD for non-target disease since SD is used as endpoint for assessment of efficacy in trials so to assign this category when no lesions can be measured is not advised.

The best overall response is the best response recorded from the start of study treatment until progression or death or discontinuation for any reason (the end of treatment taking into account any requirement for confirmation). In general, the subject's best response assignment will depend on the achievement of both measurement and confirmation criteria and will be determined by combining the subject's status of target lesions, non-target lesions, and new lesions.

- **Symptomatic Deterioration:** Subjects with global deterioration of health status requiring discontinuation of treatment without objective evidence of disease progression at that time, and not related to study treatment or other medical conditions should be reported as progressive disease due to "symptomatic deterioration." Every effort should be made to document objective progression even after discontinuation of treatment due to symptomatic deterioration. Symptomatic deterioration that may lead to discontinuation of treatment include, but is not limited to, symptoms such as:

- Weight loss > 10% of body weight.

- Worsening of disease-related symptoms (e.g., worsening dyspnea, increasing pain/increasing requirement for narcotic analgesics).
- Decline in performance status of > 1 level on ECOG scale.

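### Criterion 5 defines measurable disease by longest diameter with no lymph-node rule, so a patient whose only disease is nodes under 15 mm short axis can enrol with no target lesion under 8.2

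*Combined protocol and SAP*

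**What the plan says.** **Eligibility.** Section 5.1, criterion 5, asks for at least one lesion whose "longest diameter can be accurately measured as ≥ 20 mm with conventional techniques or as ≥ 10 mm with spiral CT". The Investigator Study Eligibility Verification Form carries the same rule: "Presence of measurable disease as defined by ≥ 1 lesion whose longest diameter can be accurately measured as ≥ 20 mm". Neither place mentions the short axis or gives nodes a different size.

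**Target lesions.** Section 8.2 measures nodes by short axis and sets three size limits: "are ≥ 10 mm (CT and MRI), ≥ 15 mm lymph nodes, > 20 mm CXR". Partial response is defined only on these lesions: "At least a 30% decrease in the sum of diameters of target lesions". The measured progression rule in 8.2 (20% over the smallest sum and at least 5 mm absolute) also uses the target-lesion sum.

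**Non-target lesions.** Section 8.3 places "lymph nodes ≥ 10 mm to < 15 mm short axis" among the non-target lesions and says that non-target lesions are not measured. For complete response, all nodes must be under 10 mm short axis.

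**Patients with non-target disease only.** Table 6 in 8.4 allows CR, non-CR/non-PD, NE or PD. It has no PR row, and its footnote says "Non-CR/non-PD is preferred over SD for non-target disease".

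**Analysis.** Section 11.1 treats every eligible patient who receives any protocol treatment as evaluable and replaces only unevaluable patients.

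**The concern.** Eligibility and response assessment use different definitions of measurable disease. The gap concerns one kind of patient: disease confined to nodes, every node below 15 mm short axis, and at least one node long enough to pass criterion 5. That patient enters properly, counts in every analysis and is not replaced, yet has no baseline sum of diameters.

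Two endpoints could be touched. For the objective response rate (secondary) and the duration of response that depends on it, the patient is judged on a different scale from the others. For the primary 18-week endpoint, progression is a qualitative judgement instead of a measured one, in groups of 20 and 18 patients decided at 3 and 4 successes.

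**Working it through.** The plan gives no figure for this point, so the check is a comparison of the rules, followed by one calculation on assumed numbers.

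**Step 1: trace one patient.** Take a patient whose only disease is a node of 18 mm longest diameter and 12 mm short axis on spiral CT.

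- Criterion 5: 18 mm ≥ 10 mm, so eligible. With conventional techniques the limit is 20 mm and this node would not pass.
- Section 8.2: 12 mm < 15 mm, so not a target lesion.
- Section 8.3: 12 mm lies in the 10 to under 15 mm band, so non-target and unmeasured.
- Table 5: every PR row needs CR or PR in target lesions, so none applies.
- Table 6: the possible outcomes are CR, non-CR/non-PD, NE and PD.

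**Step 2: response.** PR is unattainable but CR is not. For CR the 12 mm node must fall below 10 mm, a reduction of just over 2 mm, or 2/12 = 17%, with any other non-target disease gone and markers normal where applicable. PR in target lesions needs 30%. The patient loses one route to response and may have an easier one.

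**Step 3: effect on the response rate.** Assume k of the 38 patients have no target lesion, 20% of the others respond, and a fraction r of the k respond. The documents give none of these three values.

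Overall rate = [0.20 × (38 − k) + r × k] / 38

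- k = 1, r = 0: 7.4/38 = 19.5%
- k = 3, r = 0: 7.0/38 = 18.4%
- any k, r = 0.20: 20.0%
- k = 1, r = 1: 8.4/38 = 22.1%
- k = 3, r = 1: 10.0/38 = 26.3%

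The shift changes sign at r = 20%. For scale, the approximate 95% half-width of a 20% rate in 38 patients is 1.96 × √(0.20 × 0.80 / 38) = 12.7 percentage points.

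**Step 4: progression.** With no target lesion, the 20% and 5 mm rule has nothing to act on. What remains is new lesions, unequivocal non-target progression (8.3, Table 6) and symptomatic deterioration (8.4). Section 8.3 lets the treating physician's opinion prevail on non-target progression and wants the status confirmed later. Scans after every second 21-day cycle fall at about weeks 6, 12 and 18, so a judgement left for later confirmation at the third scan would coincide with the primary time point.

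**The case against.** The case for leaving the text alone has four parts.

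- Section 8.1 adopts RECIST 1.1, and an investigator who carries the nodal rule of 8.2 back to entry would not enrol such a patient. This stands in part. Section 8.1 governs response assessment, whereas criterion 5 gives its own size definition, and Appendix A has network sites register patients on the form that repeats it. Some sites may apply the nodal rule at entry and others not.
- The group may be empty. This stands: the documents give no data on sites of disease.
- The response rate is secondary and only described (11.4), and the primary endpoint needs no partial response. Both are true and limit the consequence.
- New lesions and symptomatic deterioration count as progression for every patient, with or without target lesions. This also stands. Only the measured-growth route is lost.

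Two stronger readings are tempting. A reader might infer that such a patient can only lower the response rate. Table 6 has a CR row and 8.3 sets an attainable nodal CR, so the documents do not support that. A reader might also cite a node 12 mm long and 8 mm across, which passes the size test literally. Section 8.3 regards a node of that short axis as non-pathological, so it is doubtful that anyone would enrol a patient on it as measurable disease. The 18 by 12 mm node is the fair example.

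**Conclusion.** The mismatch is real and follows from the protocol's text alone. It admits patients whom the response section cannot fully assess: node-only disease, every node under 15 mm short axis, no other lesion that qualifies. For them PR is impossible, CR remains possible and progression is not measured. The bias in the response rate has no determined direction. Under the assumptions above it lies between −1.6 and +6.3 percentage points, and the upper end needs all three of three such patients to respond.

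An effect on the 18-week result is possible but not shown. A reader might argue that one miscounted success per group would undermine the decision rule. If one patient in each group were certain to be counted a success, the chance of passing at the ineffective rate would go from 7.5% to P(Bin(19, 0.05) ≥ 2) = 24.5% in Group A, and from 9.8% to P(Bin(17, 0.10) ≥ 3) = 23.8% in Group B. That is a bound under an assumed event. Nothing in the documents says that such a patient will enrol or be miscounted.

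With the number of patients unknown and possibly zero, the severity is minor.

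**What to change.** Restate criterion 5 in 5.1 and on the eligibility form as at least one lesion that qualifies as a target lesion, in line with 8.2 and 8.6:

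- a non-nodal lesion of at least 10 mm longest diameter on CT or MRI, subject to the 8.6 condition that the minimum is twice the slice thickness when slices exceed 5 mm; or
- a lymph node of at least 15 mm short axis; or
- a chest x-ray lesion of the size given in 8.2; or
- a superficial clinical lesion of at least 10 mm by calipers.

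The last item and the slice-thickness condition need to be there; a shorter rewrite would create a new mismatch with 8.6.

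The cost is one eligibility line in two places. Sample size, visits and decision rules do not change. The downside is that a few node-only patients become ineligible.
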